4 STUDY SCHEDULE

The total study duration for each subject consists of pre-screening, screening, treatment, and follow-up periods. A study flow diagram is presented in [Figure 4-1](#).

- (1) Pre-Screening Period:** A separate Informed Consent Form (ICF) will be used for the pre-screening. The pre-screening period is designed for evaluation of histologically or cytologically confirmed locally advanced or metastatic solid tumors and CCR5 positive status by Immunohistochemistry (IHC) assay. This assay will be performed in archival tissue from previous biopsy specimens. If archival tissue is not available then, fresh core or excisional biopsy will be done. If patient qualifies, then they will undergo full screening.
- (2) Screening Period:** Screening assessments will commence after obtaining signed informed consent, and will include review of medical and medication history, demographic information and baseline disease characteristics, eligibility evaluation, physical examination, vital signs, height and weight, concomitant medications, electrocardiogram (ECG), tumor imaging assessment (prior imaging assessment within the last 3 months of the Screening Visit is acceptable), routine serum biochemical, hematologic, urinalysis, serum pregnancy (if applicable). These assessments must be conducted within 28 days of the first treatment visit.
- (3) Treatment Period:** Subjects who meet the eligibility criteria will have completed following evaluations and assessments before receiving treatment: a) review of medical and medication history; b) physical examination, vital signs and documentation of ECOG performance status; c) ECG; d) routine serum biochemical, hematologic, urine pregnancy (if applicable) and urine laboratory assessments. Additionally, a blood sample will be collected prior to treatment administration for CTC and CAML analysis.

Leronlimab (PRO 140) will be administered subcutaneously weekly by a licensed medical professional at clinic site or self-administered by subjects at home.

***Note:** All initial leronlimab (PRO 140) SC weekly injections must be administered at clinic. The remaining study treatment injections may be self-administered by subjects at home after proper training by a healthcare professional.*

Subjects will be allowed to continue treatment until any one of the following occurs: progressive disease or unacceptable toxicity or withdrawal of consent.

- (4) Follow-Up Period:** An End of Treatment (EOT) visit will be conducted 30 (\pm 3) days after the last treatment visit (i.e., after last dose of leronlimab (PRO 140). Additionally, follow-up will be done for survival status, by clinic visits or phone or another method of

contact, every 3 months (± 1 month) for 2 years after treatment discontinuation or until death, whichever occurs first.

Figure 4-1: Study Flow Diagram

[figure not shown]

Table 4-1: Schedule of Assessments

Tests and Assessments	Screening Period												Treatment Period						Follow-up Period		
	Visit	Pre-Screening Visit [1]	Screening Visit		T1	T2	T3	T4	T5	T6	T7	T8	T9	T10	T11	T12	T13	TX	Add. Rx Visits [23]	EOT	Follow-ups
Day(s)			Week 1	Week 2	Week 3	Week 4	Week 5	Week 6	Week 7	Week 8	Week 9	Week 10	Week 11	Week 12	Week 13	Week X		30 Days (±3 months after last treatment visit) [18]			
Window																		±3 days since last treatment			
Informed Consent [2]	X	X																			
Demographics and Baseline Disease Char.		X																			
Medical and Medication History [3]	X	X																			
Vital Signs [4]	X	X	X	X	X	X	X	X	X	X	X	X	X	X	X	X	X	X	X	X	
Height and Weight	X	X[5]																			
Physical Exam	X	X	X[6]	X[6]	X	X[6]	X	X[6]	X	X[6]	X	X[6]	X	X[6]	X	X[6]	X	X	X	X	
ECOG Performance Status	X	X																			
Electrocardiogram, 12-lead [7]	X	X																			
Toxicity assessment (post treatment)		X			X												X		X[19]	X[20]	
Tumor Imaging Assessment [8]		X																X		X[20]	
Complete Blood Count [9][24]		X[22]																X[22]		X	
Biochemistry [10][24]	X	X[22]																X[22]		X	
Urinalysis [11][24]	X	X[22]																X[22]		X	
Serum Pregnancy test [12]	X																				
Urine Pregnancy test [12]	X				X													X		X	
Eligibility Assessment	X	X	X																		
Enrollment / Cohort Assignment		X																			
Blood sample collection for CTC and CAML Analysis [13]	X																X		X		
Tissue for CCR5 (archival or fresh biopsy)	X[14]																				

Additional Treatment Visits (Section 4.3.2)

Tests and Assessments	Screening Period												Treatment Period												Follow-up Period	
	Visit	Pre-Screening Visit	Screening Visit [11]	T1	T2	T3	T4	T5	T6	T7	T8	T9	T10	T11	T12	T13	TX	Add. Rx Visits [23]	EOT	Survival Follow-ups						
Day(s)			Week 1	Week 2	Week 3	Week 4	Week 5	Week 6	Week 7	Week 8	Week 9	Week 10	Week 11	Week 12	Week 13	Week X										
Window																										
Ironlimab (PRO 140) administration [15]																										
Post Injection Site Evaluation by Investigator [16]																										
Injection Site Pain Assessment [17]																										
Survival status																										
Concomitant medications	X	X	X	X	X	X	X	X	X	X	X	X	X	X	X	X	X	X	X	X	X	X	X	X		
Adverse Events	X	X	X	X	X	X	X	X	X	X	X	X	X	X	X	X	X	X	X	X	X	X	X	X		

Footnotes

- [1] A separate Informed Consent Form (ICF) will be used for the pre-screening. The pre-screening period is designed for evaluation CCR5 positive status by Immunohistochemistry (IHC) assay. This assay will be performed in archival tissue from previous biopsy specimens. If archival tissue is not available then, fresh core or excisional biopsy will be done. If patient qualifies, then they will undergo full screening.
- [2] Informed consent must be obtained prior to patient participation in any protocol-related activities that are not part of routine care.
- [3] A complete review of the subject's past medical history, past surgeries, and current therapies (medications and non-medications) will be undertaken by the Investigator to check that all inclusion and no exclusion criteria have been met.
- [4] Vital signs include blood pressure, heart rate, respiration rate, and temperature will be measured at clinic visit.
- [5] Weight only
- [6] Symptom-directed physical examination at clinic visits
- [7] A 12-lead ECG will be repeated during the study only if clinically indicated and at the discretion of the treating physician.
- [8] Prior tumor imaging assessment within the last 3 months of the Screening Visit is acceptable. During the Treatment Phase, scans are to be done approximately every 3 months or according to institution's standard practice by CT, PET/CT or MRI with contrast (per treating investigator's discretion) using the same method as at baseline. Tumor measurements will be done using RECIST v1.1. To be assigned a status of PR or CR,

changes in tumor measurements must be confirmed by repeat assessments that should be performed 4-8 weeks after the criteria for response are first met. In the case of SD, measurements must have met the SD criteria at least once after study entry at a minimum interval of 4-8 weeks.

[9] Hemoglobin, Hematocrit (HCT), Red Blood Cells (RBC), White Blood Cells (WBC) with total and differential count, absolute lymphocyte count, absolute neutrophil count (ANC) and platelets.

[10] Serum Biochemistry will include:
Hepatic function indicators: total bilirubin, direct bilirubin, alkaline phosphatase, aspartate aminotransferase (AST)/SGOT, alanine aminotransferase (ALT)/SGPT, albumin and total protein.
Renal function indicators: blood urea nitrogen (BUN), creatinine
Electrolytes: sodium, potassium, chloride, calcium and bicarbonate
Other: glucose (random)

Urine samples will be tested for pH, appearance, color, specific gravity, turbidity, ketones, bilirubin, blood, glucose, protein, nitrites, urobilinogen, and leukocyte esterases. Microscopic exam includes bacteria, cast, crystals, epithelial cells, RBC and WBC.

[11] Only performed on women of childbearing potential

[12] Blood sample collection for CTC and CAML analysis to be taken prior to treatment administration at T1 and every 3 weeks thereafter, and at the end of treatment (EOT).

[13] Blood sample collection for CTC and CAML analysis to be taken prior to treatment administration at T1 and every 3 weeks thereafter, and at the end of treatment (EOT).

[14] Archival tissue (primary or metastatic site) will be collected from all patients at the pre-screening period and analyzed for presence of CCR5. Note:
If no archival tissue is available, fresh biopsy to be done of the primary or metastatic site.

[15] Leronlimab (PRO 140) is administered as subcutaneous injection in the abdomen weekly. A total of 525 mg (175 mg/mL) is delivered as two injections of 1.5 mL each on opposite sides of the abdomen.

[16] Injection Site Reaction Assessment as assessed by Investigator (or designee) at the clinic visits. Injection Site Reaction Assessment will not be applicable if leronlimab (PRO 140) is self-administered by subjects at home.

[17] Subject-perceived injection site pain (average pain since last treatment) will be assessed using the numeric pain rating scale prior to each study treatment administration which evaluates average pain since last treatment. Injection Site Pain Assessment will not be applicable if leronlimab (PRO 140) is self-administered by subjects at home.

[18] Subjects will be followed up by clinic visits or phone call or another method of contact, for survival status every 3 months (± 1 month) for 2 years after treatment discontinuation or until death, whichever occurs first

[19] All subjects will be followed for adverse events for 30 days after last dose of leronlimab (PRO 140), or until the subject starts a new treatment, whichever occurs first.

[20] Subjects who discontinue treatment for unacceptable adverse event(s) will be followed until resolution or stabilization of the adverse event (i.e. the grade is not changing). If a subject stops treatment due to unacceptable adverse event(s) but has not demonstrated disease progression, then the

subject will be followed with imaging studies every 9 weeks until the time of progression radiographically according to RECIST v1.1 criteria. In the event that a radiographic response is detected, then this event will be included as a response in the final analysis, and the time of progression used in calculation of the survival analysis.

- [21] Limited to all subsequent anti-cancer treatments.
- [22] Can be performed within 3 days prior to each treatment visit.
- [23] Subjects can continue to receive treatment until one of the following occurs: progressive disease, unacceptable toxicity, or withdrawal of consent
- [24] CBC, biochemistry, and urinalysis testing schedule (i.e., every 21 days) is allowed to be modified by the treating oncologist (or Investigator) based on standard of care chemotherapy regimen. Must be performed at least once every 28 days (4 weeks).

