6.1.3. Leronlimab (PRO 140) - Administration

Guidelines for dose preparation can be found in the pharmacy manual.

Leronlimab (PRO 140) will be provided to the administering personnel in single-use syringes prepared from vials of study drug stored at 2-8°C at the site pharmacy prior to use.

A 25-gauge needle will be used for Leronlimab (PRO 140) administration. PRO 140 should be administered slowly over 15 seconds per mL. The IP should not be kept in syringe for longer than 60 minutes.

Following each SC delivery of drug, careful examination will be made to assess the appearance of any study drug Injection Site Reactions (ISRs) as per CTCAE v5.0

All doses of study drug will be prepared by either the credentialed pharmacist or qualified medical professional and will be administered as SC injection by a licensed medical professional when leronlimab (PRO 140) is administered at clinic site. Self administration by subjects at home is allowed at certain visits.

All initial leronlimab (PRO 140) SC weekly injections must be administered at clinic. The remaining study treatment injections may be self-administered by subjects at home after proper training by a healthcare professional.

Note: It is preferred that the same injection site be used throughout the study. At the same time, it is not recommended to inject the study drug into areas where skin shows signs of a previous injection site reaction. It is advised to change the injection site if any previous injection site reaction remains unresolved.

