6.1.5. Leronlimab (PRO 140) - Dose Modifications

The dose interruption and permanent discontinuation for any toxicity are described below.

Dose interruption: Refer to [Table 6-2](#) below. Recovery to acceptable levels must occur to allow leronlimab (PRO 140) continuation. Any adverse event deemed to be related to leronlimab (PRO 140) that requires a dose hold of more than 21 days will result in permanent discontinuation of leronlimab (PRO 140).

Table 6-2: Leronlimab (PRO 140) Dose Modification and Management for Injection Site Reactions

CTCAE Grade	Treatment Modifications
Grade 1	No dose adjustment is required.

Grade 2	First Occurrence: No dose adjustment is required. Second Occurrence of the same event: Closely follow-up for resolution of the AE to Grade ≤ 1
Grade 3	Withhold treatment until symptoms resolve to: • Grade 1 or less
Grade 4	Study treatment will be permanently discontinued

Permanent discontinuation of Treatment: If toxicity is reported at 525mg dose.

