7.13 POST-INJECTION EVALUATION AND INJECTION SITE REACTION ASSESSMENT

[figure not shown]
At each treatment visit, an injection site reaction assessment will be made for the current and previous injection sites. Injection site reaction assessments are recorded by the Investigator starting after the first injection is given. Subject will be observed at approximately 30 minutes post-injection or longer if necessary for injection site reaction as per CTCAE v5.0. Refer to [Sections 9.2.6](#) for more details.

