9.2.6. Injection-site reactions

Injection-site reactions thought to be directly related to the injection are considered to be AEs of special interest, and will be assessed as per CTCAE v5.0.

For subjects who develop Grade 1 or Grade 2 events, therapy will be continued as per protocol. If a subject chooses to discontinue study treatment, the site should notify the protocol team leadership, and encourage the subject to complete any remaining study visits until the toxicity resolves.

For subjects who develop Grade 3 events following study drug injection, the subject should be reevaluated closely until the AE returns to Grade 1 or less, at which time study treatment may be reintroduced at the discretion of the site investigator. If the same Grade 3 AE recurs following the next administration of study drug, study treatment must be permanently discontinued. Subjects experiencing Grade 3 AEs requiring permanent discontinuation of study treatment should be followed closely for resolution of the AE to Grade 1 or less and the team leadership must be notified.

For Grade 4 events permanently discontinue therapy.

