8.3.9 Post Injection Site Evaluation by Investigator

All data from post injection site evaluation by investigator will be presented as a by-subject listing and/or summarized descriptively.

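### Injection-site reactions have no scheduled assessment at home doses, against Sections 6.1.3 and 7.13, so mild reactions may be missed and the reported rate may be too low by an unknown amount

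*Protocol*

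**What the plan says.** **Where doses may be given.** Dosing is weekly (Table 6-1). Section 6.1.3 says: "All initial leronlimab (PRO 140) SC weekly injections must be administered at clinic". The rest may be self-injected at home after training. How many injections count as initial is not stated.

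**The exemption.** Table 4-1, footnote 16: "Injection Site Reaction Assessment will not be applicable if leronlimab (PRO 140) is self-administered by subjects at home". Footnote 17 says the same of pain: "Injection Site Pain Assessment will not be applicable if leronlimab (PRO 140) is self-administered by subjects at home". The SAP's copy of the schedule (Appendix 1) carries both sentences, as its footnotes 15 and 16.

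**The texts that require assessment.** Section 6.1.3 calls for a careful look for reactions after each subcutaneous delivery. Section 7.13 says: "At each treatment visit, an injection site reaction assessment will be made for the current and previous injection sites". Section 4.3.2 lists the investigator's post-injection site evaluation among the procedures from T2 onward and makes no exception for home dosing.

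**What depends on the result.** Section 9.2.6: "Injection-site reactions thought to be directly related to the injection are considered to be AEs of special interest". For a Grade 3 reaction, Table 6-2 says: "Withhold treatment until symptoms resolve to" Grade 1 or less. Section 9.2.6 adds: "If the same Grade 3 AE recurs following the next administration of study drug, study treatment must be permanently discontinued".

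**The analysis.** SAP 8.3.9: "All data from post injection site evaluation by investigator will be presented as a by-subject listing and/or summarized descriptively". SAP 8.3.10 treats pain the same way. Neither section names a denominator or separates clinic from home doses.

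**The concern.** Two instructions cannot both be followed. A site that obeys Section 6.1.3 examines the subject after every dose; a site that obeys footnote 16 does not assess home doses. Different sites may resolve this differently. Within one subject, clinic doses are then observed by an investigator and home doses depend on what the subject reports.

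Tolerability is a secondary objective, and Section 6.1.4 says that tolerability of repeated subcutaneous dosing is judged by injection-site pain. The dose rose from 350 mg to 525 mg under version 2.0 of the protocol, and Section 6.1 allows 525 mg as either two 1.5 mL injections or one of 3 mL. These are reasons to want an injection-site table that can be interpreted. As planned, a reader of that table could not tell a dose with no reaction from a dose that nobody assessed.

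The recurrence rule in Section 9.2.6 also looks at what happens after the next administration. It works best if ascertainment is equally good wherever that dose is given.

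**Working it through.** The plan states no expected reaction rate, no expected share of home doses and no power figure, so there is no figure of its own to reproduce.

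**1. The texts side by side.**
- Section 6.1.3 (after each delivery) and footnote 16 (not applicable at home) contradict each other for home doses.
- Section 7.13 can be partly reconciled with footnote 16: nothing is done at the home injection, and the earlier site is inspected at the next clinic visit. On that reading the home dose gets a delayed check. The footnote does not say so, and a reaction that has cleared by then leaves nothing to inspect.

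**2. Doses with no scheduled assessment at dosing, T1 to T13.** Section 4.3.2 puts the physical examination, ECOG and laboratory samples at T4, T7, T10 and every 3 weeks after. Share = (13 − clinic doses) / 13.

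| Doses given in clinic | Clinic | Home | Share at home |
|---|---|---|---|
| T1–T4, T7, T10, T13 | 7 | 6 | 6/13 = 46% |
| T1, T4, T7, T10, T13 | 5 | 8 | 8/13 = 62% |
| T1 only | 1 | 12 | 12/13 = 92% |

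On the 3-weekly pattern over 52 weeks, 18 doses are in clinic and 34 at home (34/52 = 65%). The three rows are scenarios for a subject who uses home dosing whenever that reading allows. A subject who always attends has 0%.

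**3. What this could do to the recorded incidence.** Both inputs here are assumptions: p, the chance of a reaction per dose, and c, the fraction of home-dose reactions that still reach the record through adverse event reporting or a later site check. Doses are taken as independent. With 5 clinic and 8 home doses:

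- every dose assessed: 1 − (1 − p)^13
- as planned: 1 − (1 − p)^5 × (1 − pc)^8

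| p | Every dose assessed | c = 0.8 | c = 0.5 | c = 0 | Ratio at c = 0 |
|---|---|---|---|---|---|
| 0.02 | 23.1% | 20.6% | 16.6% | 9.6% | 0.42 |
| 0.05 | 48.7% | 44.2% | 36.8% | 22.6% | 0.46 |
| 0.10 | 74.6% | 69.7% | 60.8% | 41.0% | 0.55 |
| 0.20 | 94.5% | 91.9% | 85.9% | 67.2% | 0.71 |

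At c = 1 there is no loss. The documents do not fix p or c, so the table shows a range and is not an estimate. The choice of denominator also matters. Take p = 0.10 and c = 0. Reactions per injection given are expected at 5 × 0.10 / 13 = 3.8%, while reactions per injection assessed remain at 10%.

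**4. The pain score.** Footnote 17 has the score taken before an administration, covering average pain since the previous one, and skipped when that administration is at home. On the 3-weekly pattern, the scores at T4, T7, T10 and T13 describe T3, T6, T9 and T12, all home doses. Pain after T1, T4, T7 and T10, all clinic doses, would be scored before T2, T5, T8 and T11. Those are home doses, so the score is skipped. Read literally, the gap falls on clinic doses as well as on some home doses.

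**The case against.** The strongest reply is that the dose rules do not depend on the post-injection form. Table 6-2 and Section 9.2.6 act on the CTCAE grade of an adverse event. Section 9.1 elicits adverse events by direct questioning and subject report, Section 9.2 requires a grade for each, and the adverse event row of Table 4-1 has no home exemption. This stands. A reader might infer that a home dose cannot trigger withholding or discontinuation. The documents do not support that, because a reported Grade 3 reaction after a home dose would be graded and acted on.

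A reader might also infer that unassessed doses are counted as free of reaction, so that the rate is certainly too low. That is not supported either. SAP 7.4 and protocol Section 8.6.3 rule out imputation, and the adverse event tables in SAP 8.3.1 count subjects, not injections. The SAP is silent on the injection denominator, and silence is not a rule that scores missing as zero.

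Three further points reduce the weight of the concern:
- Section 7.13 gives home doses a delayed check if it is followed.
- Section 6.1.3 speaks of initial injections in the plural, so the T1-only case is an extreme. In the mildest scenario above, fewer than half of the doses are at home.
- The 525 mg dose is not new: Section 1.5 cites more than 250 subjects exposed, and Section 1.4.14 reports comparable reactions at 350, 525 and 700 mg in an HIV study.

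What the reply leaves standing is the textual conflict, the unequal ascertainment, and an analysis section that would not reveal either.

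**Conclusion.** The point holds as a conflict in the text and a difference in ascertainment. Footnote 16 contradicts Section 6.1.3 and is hard to square with Section 7.13. For a subject who uses home dosing, about 46% to 92% of the first 13 doses have no scheduled reaction assessment at the time of dosing, and 62% on the 3-weekly pattern. These figures rest on how many injections count as initial, which the protocol does not define, and on uptake of home dosing, which it does not predict.

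The reaction rate may be understated, chiefly for mild or transient reactions that clear before the next visit. The amount is unknown. Under assumed per-dose probabilities of 0.02 to 0.20, it runs from nothing, with full capture, to a recorded per-subject incidence of 42% to 71% of the true one, with no capture at home. To state that the rate is understated would go beyond the documents. The pain score has its own gap, which can leave clinic doses such as T1 unscored.

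**What to change.** **Protocol.** Reconcile footnotes 16 and 17 of Table 4-1 with Sections 6.1.3 and 7.13, and state which injections are the initial ones. For data capture, record at the next scheduled clinic visit the CTCAE grade of any reaction and the pain score for each home injection since the last visit. For pain, include the clinic injection that opened the interval, so that T1 is not lost. Make the same change in the SAP's copy of the schedule.

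**SAP 8.3.9 and 8.3.10.** Report the number of injections assessed next to the number given, use assessed injections as the denominator, and show clinic and home doses separately.

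**Cost.** Added data items at visits already in the schedule. The case report form is not among the documents, so the exact effort cannot be stated. SAP Section 12 describes the SAP as a first draft, so its text can still be changed easily. The drawback is recall: with 3-weekly visits, the older of two home doses is about two weeks back (T2 asked about at T4) and the preceding clinic dose about three. The existing pain item already relies on recall since the last treatment, and the separate display lets a reader discount home-dose data. No dose or withholding rule is changed.
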